Statistical Considerations	
Primary Efficacy Endpoint Analysis
 
The primary efficacy endpoint is defined as the mean HGB change from Baseline (mean pretreatment HGB) to the mean HGB from Weeks 24-36 (inclusive).
 
The primary analysis will use an analysis of variance (ANOVA), stratified by the randomization strata with strata weighted by the stratum size.
 
A 2-sided, 95% confidence interval will be calculated for the difference between the vadadustat group and control group. Noninferiority of vadadustat will be established if the lower limit of this confidence interval is ≥ -0.5 g/dL.
 
MACE Analysis
 
The MACE endpoint (adjudicated result) will be analyzed as the time from first dose of study medication to first MACE. Subjects who have not experienced an adjudicated MACE by study closure will be censored as of their last assessment time.
 
Major adverse cardiovascular events will be analyzed using a stratified Cox proportional hazards model with a model containing treatment group. The randomization strata will be used in this analysis. The primary MACE analysis will take place at study conclusion and will be based upon all subjects in the safety population. The hazard ratio (vadadustat/control) will be estimated, together with its 95% confidence interval. As this individual study has not been powered to provide a stand-alone estimate of the hazard ratio for MACE, this interval will be considered as descriptive. The time to first MACE will also be graphically presented using Kaplan-Meier curves.
 
The primary analysis for MACE will be performed using the safety population. These analyses will be repeated with censoring occurring 4 weeks following early discontinuation of study medication.
 
An independent statistical analysis center will perform analyses in support of the Independent Data Monitoring Committee (IDMC).

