7.5.2 Subject Completion

A subject will be considered as having completed the study, regardless of whether they are on or off study medication (vadadustat or darbepoetin alfa), if the subject is followed until global study completion (end of trial). The table outlines the different categories of subjects and handling the global study completion activities.

Subject Status at time of Global Study Completion	End of Treatment (EOT)	End of Study (EOS)
Subject on study medication (includes those on temporary interruption)	After announcement of global study completion: 
 • Perform EOT visit • Perform the Follow-up visit 4 weeks after EOT visit and include End of Study (EOS) subject status 	Not applicable The EOS subject status will be captured as part of the Follow-up visit
Subject permanently discontinued study medication and continues to be followed in the study	At time of permanent discontinuation of study medication: 
 • Perform EOT visit • Perform the Follow-up visit 4 weeks after EOT visit 	Optimal data collection would include the following assessments: 
 • EOS subject status (must collect at minimum) • MACE Endpoint Questionnaire • AE Assessment
Subject Lost to Follow-up	Not applicable	Work with third party vendor to ascertain vital status and complete EOS subject status If subject-site contact is reestablished and possible, collect available information for EOS subject status
Subject Withdrawn Consent	Not applicable	Complete the EOS subject status form at time of withdrawal of consent, absolute refusal of ALL methods of MACE and health status follow-up

Subject Death	Not applicable	Complete the EOS subject status form at the time of death (see Section 10 Adverse Events for more details on other actions related to reporting a death)
---------------	----------------	--

The need for rescue therapy does not constitute study completion and is not a criterion for subject withdrawal from the study. Also, the occurrence of a safety endpoint, or if a subject progressed to chronic dialysis dependent CKD (DD-CKD), does not constitute study completion and is not a criterion for subject withdrawal from the study or study medication (vadadustat or darbepoetin alfa).

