7.5.5.1 Temporary Interruption of Study Medication

Subjects who temporarily interrupt study medication (vadadustat or darbepoetin alfa) treatment after the first dose and prior to completion of the study will continue with study visits and assessments. Unless contraindicated, treatment should be resumed wherever possible and routinely considered at every visit following study medication discontinuation. If a subject does not return for a scheduled visit, every effort should be made to contact the subject. If a subject's study medication has been temporarily interrupted for more than 60 days, the Investigator should contact the Medical Monitor before resuming study medication.

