8.5.2 Erythropoiesis-stimulation Agents

For all subjects, it is recommended that no additional ESA doses be administered after Screening visit 2 (SV2) and prior to the Randomization visit.

Non-protocol ESAs are prohibited from Randomization until the end of the study, unless the subject is receiving ESA rescue therapy, interrupts study medication for other reasons, or permanently discontinues study medication. Reasons for ESA use will be captured in the appropriate CRF (e.g., adverse event, inadvertent administration, etc.).

Concomitant use of an ESA with study medication is strictly prohibited.

In the setting of ESA rescue therapy, the initial dose of ESA rescue therapy may be administered on the same day as the last vadadustat dose prior to vadadustat dose interruption (see [Section 7.5.5.1, Temporary Interruption of Study Medication](#)) if deemed medically necessary at the discretion of the Investigator. Guidelines for ESA administration as rescue therapy are provided in [Section 8.4.7.1, ESA Rescue](#).

All efforts will be made to avoid inadvertent administration of ESAs resulting from following routine ESA hemodialysis protocols (e.g., dialysis center ESA protocols for subjects on hemodialysis). If ESA is inadvertently administered to subjects actively receiving vadadustat treatment, vadadustat treatment will be stopped and the event will be reported as a protocol deviation

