11.7.1 Analysis of MACE and Expanded MACE Components

The primary safety endpoint, time to the first adjudicated MACE, will be analyzed as [date of the first MACE minus the date of randomization +1]. A MACE is defined as all-cause mortality, non-fatal myocardial infarction, or non-fatal stroke. Subjects who have not experienced a MACE by study closure will be censored on the date of their last study assessment. The hazard ratio (vadadustat/darbepoetin alfa) and its 95% confidence interval will be obtained from a stratified Cox proportional hazards model. As this study has not been designed to provide a stand-alone assessment of MACE, this analysis will be considered a descriptive analysis. A similar analysis as described for the primary analysis of the MACE endpoint will be performed with censoring of subjects 4 weeks following discontinuation of study medication if they did not have a MACE prior to that time.

An additional analysis as described for the primary analysis of the MACE endpoint will be performed with censoring at time of chronic dialysis initiation for subjects who have progressed to chronic dialysis and who did not have a MACE prior to that time.

The following safety endpoints will also be summarized using time to event methods as for MACE:

- 1) Individual components (all-cause mortality, non-fatal myocardial infarction, non-fatal stroke) of MACE
- 2) Thromboembolic events (defined as arterial thrombosis, DVT, PE, or vascular access thrombosis)
- 3) Hospitalization for heart failure

- 4) Expanded MACE, defined as all-cause mortality, non-fatal myocardial infarction, non-fatal stroke, hospitalization for HF, or thromboembolic event

For these endpoints the incidence ("yes"/"no") of the endpoint will be presented for each treatment arm. Kaplan-Meier curves will be presented for each endpoint as the time of endpoint free survival (ie, time until endpoint or death).

The primary MACE analysis will be based upon all events that accrue over the 2 NDD-CKD studies (Studies AKB-6548-CI-0014 and AKB-6548-CI-0015) (see [Section 11.1.2, Sample Size for the Primary Safety Endpoint](#)).

The SAP for this pooled MACE assessment in NDD-CKD subjects provides details of the primary analyses for MACE, for individual components of MACE, and for an expanded version of MACE. Details of sensitivity analyses and subgroup analyses are also provided in the MACE SAP.

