### 6.3.9 Rescue Therapy: Series of Definitions

Rescue will be defined from narrow to broad, based on the type, timing, intensity, and reason for treatment. These treatments may be considered rescue therapy for anemia secondary to chronic kidney disease: ESA medication, and RBC transfusion.

The possible reasons for such treatments include:

- Investigator-ordered rescue (per protocol for worsening of anemia),
- Adverse events (unrelated to anemia),
- Maintenance during prolonged interruption of study treatment, and
- Inadvertent use (at hospital or dialysis center).

If a given therapy starts the same day as permanent discontinuation of study drug, then that therapy will be considered on treatment for rescue definitions.

For the vadadustat arm, any use of ESA may be considered rescue. For the control arm, the study drug itself is an ESA and so is not necessarily rescue, yet change to another ESA may be considered rescue. Because darbepoetin alfa is titratable, increase in dose is not considered rescue unless the investigator specifically designates it as such; however, increases in dose relative to last dose will be characterized in three categories by percentage increase: <50%,

Statistical Analysis Plan AKB-6548-CI-0014 and AKB-6548-CI-0015

$\geq 50\%$  and  $< 100\%$ , and  $\geq 100\%$ . Subjects will be presented by their maximum category of increase within each of the four analysis time periods in Year 1 (see [Section 5.1](#)). All ESA use will be converted to IV epoetin alfa equivalents.

The CRFs collect reasons for ESA medication and RBC transfusion. The series of rescue definitions are defined as follows:

- Narrow: Rescue for worsening anemia with ESA medication or RBC transfusion defined in [Section 6.3.7](#) and [Section 6.3.8](#), not starting after permanent study treatment discontinuation.
- Broad-on-treatment: Any exposure to ESA medication (aside from darbepoetin alfa not designated as rescue in the control arm) or RBC transfusion for any reason not starting after permanent study treatment discontinuation.

In addition to the sensitivity analyses ([Section 9.1.4](#)), the report will include a summary of the incidence, timing, duration, intensity, and frequency for each definition of rescue, including a Kaplan-Meier plot of time to first rescue.

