#### **3.2.2 Time to MACE Within 4 Weeks of End of Treatment**

Only a MACE that occurs up to and within 28 days inclusive after permanent discontinuation of study treatment (End of Treatment, EOT) will be included as a MACE Within 4 weeks of End of Treatment.

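### The supportive on-treatment MACE analysis starts its 28-day cut-off at permanent discontinuation, so off-drug time during a temporary interruption of any length counts as on-treatment

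*Protocol*

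**What the plan says.** The synopsis sentence "These analyses will be repeated with censoring occurring 4 weeks following early discontinuation of study medication" stands in the original protocol and is unchanged in Amendment 7-COL. Amendment 7-COL section 11.7.1 similarly plans "censoring of subjects 4 weeks following discontinuation of study medication if they did not have a MACE prior to that time". Neither says permanent or temporary, and the ESA rescue text (8.4.7.1) applies the verb discontinue to a temporary stop, so the protocol wording does not fix the starting point.

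MACE SAP 3.2.2 does fix it: "Only a MACE that occurs up to and within 28 days inclusive after permanent discontinuation of study treatment" is counted, and that date is equated with EOT. The table in MACE SAP 4.6 uses four weeks from EOT for both the event and the censoring date.

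Four provisions bear on what happens before EOT:

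- **Length.** Protocol 7.5.5.1 sets no maximum for a temporary interruption. If "study medication has been temporarily interrupted for more than 60 days, the Investigator should contact the Medical Monitor before resuming study medication".
- **Status.** In the protocol 7.5.2 table, one category at global study completion is "Subject on study medication (includes those on temporary interruption"). These subjects have their EOT visit only after completion is announced. Section 9.3.12 agrees.
- **ESA use.** Protocol 8.5.2 prohibits non-protocol ESAs "unless the subject is receiving ESA rescue therapy, interrupts study medication for other reasons, or permanently discontinues study medication".
- **Foreseen reason.** Main SAP 6.3.9 lists "Maintenance during prolonged interruption of study treatment" among the possible reasons for ESA or transfusion.

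**The concern.** The primary MACE analysis keeps all off-drug and post-rescue events by design (protocol 11.5). In a noninferiority safety comparison, a reader looks to the on-treatment version to see whether off-drug time has blurred a difference. As defined, that version still contains some off-drug time. A vadadustat subject can stop taking tablets, possibly receive an ESA (the control drug class), never formally discontinue, and be counted as on vadadustat to the end of the study.

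No other planned MACE analysis covers this. Protocol 11.7.1 adds a version censored at chronic dialysis, but none cuts at the last actual dose, at interruption or at the start of an ESA. For haemoglobin the plan does handle the related problem: main SAP 9.1.5 sets values within four weeks of rescue to missing. At stake is how a supportive safety result is read, not the primary conclusion.

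**Working it through.** **1. The plan's own figure.** Inputs from MACE SAP 2.5.1: margin 1.25, true HR 1.0, two-sided 95% interval, 80% power; allocation is 1:1. Events = 4 × (1.960 + 0.842)² / (ln 1.25)² = 31.40 / 0.0498 = 631, as stated. With 631 events, power is 90.9% at margin 1.30, and 93.1% at margin 1.25 if the HR is 0.95. Both agree with the plan.

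**2. Effect of counting interrupted time.** To first order, with H the true on-drug HR, fv and fc the interrupted shares of counted time on vadadustat and control, and r the hazard while interrupted relative to control on drug:

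observed HR = [(1 − fv)·H + fv·r] / [(1 − fc) + fc·r]

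The documents give none of fv, fc or r, so all three are assumptions.

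| Assumption | Substitution | Observed HR |
|---|---|---|
| H = 1.25, r = 1, fv = 5% | 0.95 × 1.25 + 0.05 | 1.238 |
| H = 1.25, r = 1, fv = 10% | 0.90 × 1.25 + 0.10 | 1.225 |
| H = 1.25, r = 1, fv = 20% | 0.80 × 1.25 + 0.20 | 1.200 |
| H = 1.25, r = 1, fv = 30% | 0.70 × 1.25 + 0.30 | 1.175 |
| H = 0.80, r = 1, fv = 10% | 0.90 × 0.80 + 0.10 | 0.820 |
| H = 1.25, r = 2, both arms 20% | 1.40 / 1.20 | 1.167 |
| H = 1.25, r = 2, vadadustat only 20% | 0.80 × 1.25 + 0.20 × 2 | 1.400 |
| H = 1.25, r = 2, 20% v 10% | 1.40 / 1.10 | 1.273 |
| H = 1.00, r = 2, 20% v 10% | 1.20 / 1.10 | 1.091 |
| H = 1.00, r = 2, 5% v 10% | 1.05 / 1.10 | 0.955 |

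With r = 1 the denominator is 1, so the control share does not matter. With equal shares f and equal r, the expression is a weighted average of H and 1 (weights 1 − f and f·r), so it always moves towards 1. When interruption carries raised risk and is unequal between arms, it can move away from 1.

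**3. What this could do to an upper limit, as illustration only.** Chance that the upper 95% limit is below 1.25 = Φ[(ln 1.25 − ln HRobs) × √(D/4) − 1.96]. At a true on-drug HR of 1.25 this is 2.5% with no interrupted time. With r = 1 and D = 631 it is 4.4% at 10% and 7.4% at 20%. With an assumed D = 450 it is 4.0% and 6.3%. The on-treatment analysis counts fewer events than the planned 631.

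**The case against.** Much of the case on the other side stands.

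- **Interruption is meant to be short.** Protocol 7.5.5.1 asks that treatment resume wherever possible and be considered at every visit. Section 8.4.7.1 stops ESA rescue at a haemoglobin threshold and gives restart intervals of 2, 7 or 14 days. A subject off drug from early on to study end is a worst case, and nothing shows it would be common. This limits the likely size, but the definition still has no limit.
- **Frequent ESA use.** A reader might infer that interrupted vadadustat subjects are usually on an ESA. The documents only permit this (protocol 8.5.2) and list it as possible (main SAP 6.3.9). No frequency is given, and some interruptions, such as those for raised transaminases (10.1.1), need no ESA.
- **One-way dilution.** A reader might infer that the bias always runs towards 1 because control subjects stay on their drug class. Darbepoetin subjects are interrupted too, and if interruption marks illness the direction can reverse, as the table shows.
- **No decision rule.** The 1.25 and 1.30 limits apply to the primary analysis (MACE SAP 4.4). The four-weeks-from-EOT analysis is outside the hierarchy in 4.5. The step 3 probabilities are therefore not error rates of the plan.
- **Partly visible already.** Main SAP 6.3.5, 6.3.8 and 6.3.9 summarise interruptions, ESA episodes and rescue by arm. But 6.3.5 plans percentages of subjects interrupted, which do not show how much MACE follow-up was off drug.

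**Conclusion.** The point holds for the supportive analysis in MACE SAP 3.2.2 and 4.6. An analysis meant to isolate risk on drug can include off-drug time of any length, because its clock starts only at permanent discontinuation. The protocol synopsis and 11.7.1 do not state that starting point.

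Size and direction cannot be fixed from the documents. A true 1.25 seen as 1.225 or 1.20 assumes control-like risk while interrupted and shares of 10% or 20%. Balanced interruption also pulls towards 1. Unequal interruption that marks illness can push the estimate away from 1, or make a null effect look favourable. That uncertainty is itself a reason to define exposure from dosing.

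The documents do not support reading this as a flaw in the primary MACE comparison or an inflated error rate for the noninferiority claim. It is a cheap improvement to a secondary safety result.

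**What to change.** In MACE SAP 3.2.2 and 4.6, add an on-treatment analysis built from dosing records, with the same rule in both arms. Censor at the earlier of EOT + 28 days and the day on which a continuous gap since the last actual dose reaches a prespecified length. Sixty days is an example, matching the protocol's own contact threshold. The length must exceed the planned darbepoetin dosing interval, so that normal spacing is not read as a gap. This is an analysis definition and changes no treatment rule.

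Count every event up to that day and do not backdate. Censoring at day 28 only when a gap later exceeds 60 days would look ahead: a death on day 45 would count, while a subject alive and still off drug at day 61 would be censored at day 28.

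Keep the EOT-based version as a second row. Report interrupted person-time and ESA use by arm. Make the protocol synopsis and 11.7.1 name the same starting point as MACE SAP 3.2.2. Settle all this before the MACE SAP is signed, which its section 1 places ahead of database lock and unblinding.

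The cost is SAP wording and one derived variable from the eCRF dosing periods already used for calculated compliance (main SAP 4.1). The new analysis will have slightly fewer events and a wider interval, and censoring at a dosing gap may be informative. That is why both versions should be shown.

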3 LIST OF ABBREVIATIONS

ACTH	adrenocorticotrophic hormone
AE	adverse event
ALT	alanine aminotransferase (SGPT)
ANOVA	analysis of variance
AST	aspartate aminotransferase (SGOT)
BUN	blood urea nitrogen
C	Celsius
CBC	complete blood count
CHF	congestive heart failure
CKD	chronic kidney disease
CKD-EPI	Chronic Kidney Disease Epidemiology Collaboration
CMH	Cochran-Mantel-Haenszel
CPK	creatine phosphokinase
CRF	case report form
CRO	contract research organization
CS	clinically significant
CV	cardiovascular
CVD	cardiovascular disease
dL	deciliter
DVT	deep venous thrombosis
EAC	Endpoint Adjudication Committee
ECG	electrocardiogram
EDC	electronic data capture
eGFR	estimated glomerular filtration rate
EOT	end of treatment
EPO	erythropoietin
ESA	erythropoiesis-stimulating agent
ESRD	end-stage renal disease
EU	European Union
F	Fahrenheit
FDA	Food and Drug Administration
g	gram
GCP	Good Clinical Practice
GFR	glomerular filtration rate
GMP	Good Manufacturing Practice
HA	health authority
HDL	high-density lipoprotein
HGB	hemoglobin
HIF	hypoxia-inducible factor
HIFPH	hypoxia-inducible factor prolyl-hydroxylase
HIF-PHI	hypoxia-inducible factor prolyl-hydroxylase inhibitor
IC ₅₀	50% inhibitory concentration
ICH	International Conference on Harmonization

IDMC	Independent Data Monitoring Committee
IDMS	isotope dilution mass spectrometry
IEC	independent ethics committee
INR	international normalized ratio
IRB	institutional review board
IV	intravenous(ly)
IWR	interactive web response
JSDT	Japanese Society for Dialysis Therapy
JSN	Japanese Society of Nephrology
KDIGO	Kidney Disease: Improving Global Outcomes
kg	kilogram
LDH	lactate dehydrogenase
LDL	low-density lipoprotein
LLN	lower limit of normal
MACE	major adverse cardiovascular events
MCH	mean corpuscular (cell) hemoglobin
MCHC	mean corpuscular (cell) hemoglobin concentration
MCV	mean corpuscular (cell) volume
MedDRA	Medical Dictionary for Regulatory Activities
μM	micromolar
mg	milligram
mL	milliliter
mRNA	messenger ribonucleic acid
MTD	maximum tolerated dose
NDD-CKD	non-dialysis dependent chronic kidney disease
ng	nanogram
PD	pharmacodynamics(s)
PE	pulmonary embolism
PHD	prolyl 4-hydroxylase domain
PK	pharmacokinetic(s)
PP	per protocol
PT	prothrombin time
PTT	partial thromboplastin time
QA	quality assurance
QC	quality control
RBC	red blood cell
RDW	red cell distribution width
ROW	rest of world
SAE	serious adverse event
SAP	Statistical Analysis Plan
SC	subcutaneous(ly)
SGOT	serum glutamic oxaloacetic transaminase (AST)
SGPT	serum glutamic pyruvic transaminase (ALT)
SmPC	summary of product characteristics
SV	Screening visit
TIBC	total iron binding capacity

TREAT	Trial to Reduce Cardiovascular Events with Aranesp Therapy
TSAT	transferrin saturation
uACR	urine albumin-to-creatinine ratio
ULN	upper limit of normal
US	United States
VEGF	vascular endothelial growth factor
WBC	white blood cell
WHO	World Health Organization

4 BACKGROUND INFORMATION

Chronic kidney disease (CKD), defined as the presence of kidney damage or a decreased level of kidney function, is a major public health problem worldwide. Globally, CKD is estimated to affect between 8-16% of the population (Jha et al. 2013; KDIGO 2013). At the most advanced stages of CKD, end-stage renal disease (ESRD), patients require chronic dialysis or kidney transplantation to sustain life. Chronic kidney disease is not only a cause of ESRD, but is also a significant risk factor for cardiovascular disease (CVD), infection, cancer, and mortality (Iseki and Kohagura 2007).

Renal anemia often develops during the progression of CKD and is present in almost all patients with ESRD. Anemia is defined as a decrease in circulating red blood cell (RBC) mass that is usually detected by low hemoglobin (HGB) concentration. The causes of anemia in CKD include blood loss, shortened RBC lifespan, iron deficiency, erythropoietin (EPO) deficiency, and inflammation (Nurko 2006). Although many factors contribute to anemia in CKD, it occurs primarily due to an inadequate synthesis of EPO by the kidneys, leading to a deficiency in the production of RBC progenitor cells by the bone marrow. Also contributing to anemia in CKD are impaired iron homeostasis and iron loss, which often necessitate iron supplementation (Nurko 2006). Anemia in CKD patients usually occurs when the glomerular filtration rate (GFR) falls below 60 mL/min/1.73 m², and is present in >90% of the patients undergoing dialysis (CKD Stage 5) (Goodkin et al. 2011).

The main impact of anemia on organ function is reduced oxygen delivery to tissues leading to a constellation of symptoms including fatigue, shortness of breath, and exercise intolerance (Stauffer and Fan 2014). In patients with anemia related to CKD, compensatory changes occur in cardiac structure and function, including an increase in cardiac output, the development of left ventricular hypertrophy, and, eventually, the development of heart failure (Metivier et al. 2000). Risk of stroke also increases with anemia, which may be an underlying mechanism leading to stroke in CKD (Abramson et al., 2003; Iseki and Kohagura 2007). Other consequences from anemia in CKD patients include impaired cognitive function, sleep disorders, and depressed immune function, which can impact the quality of life in these patients (Iseki and Kohagura 2007; NICE 2011). Overall, anemia contributes to a poorer prognosis in patients with CKD (Nurko 2006; Iseki and Kohagura 2007).

Erythropoiesis-stimulating agents (ESAs) administered either intravenously (IV) or subcutaneously (SC), along with oral or IV iron therapy, are currently the cornerstones for treating anemia in patients with CKD. Treatment with exogenous recombinant ESAs can raise HGB levels, relieve symptoms, and reduce the complications of anemia, including RBC transfusions which carry the risks of infection, iron overload, and impact candidacy for kidney transplantation.

Clinical practice guidelines and prescribing information for approved ESAs and guidelines provided by the United States (US) Food and Drug Administration (FDA), the European Union (EU), the Japanese Society of Nephrology, and the Japanese Society for Dialysis Therapy Guideline Committee differ slightly in their recommendations for treatment of renal anemia, as summarized in Table 1.

Table 1 Treatment Guidelines and Prescribing Information for Renal Anemia in NDD-CKD

KDIGO guidelines	Treatment should occur in symptomatic patients and when HGB generally falls below 10 g/dL (Kidney Disease: Improving Global Outcomes [KDIGO] 2012).
US darbepoetin alfa label	Same as other approved ESAs, but also recommend that if HGB exceeds 10 g/dL in adults not on dialysis, the dose of ESA should be reduced or interrupted (Aranesp® US Package Insert 2015).
EU practice guidelines	Recommend that in high-risk patients with NDD-CKD, treatment with ESAs should be initiated when the HGB levels are between 9 g/dL and 10 g/dL, although in low-risk patients and those in whom a clear benefit of quality of life can be foreseen, the initiation of ESA therapy could be considered at higher HGB levels (Locatelli 2013).
Japan practice guidelines	JSDT recommends that ESA treatment be initiated when HGB is below 11 g/dL following a diagnosis of renal anemia in NDD-CKD. JSN 2013 does not provide a clear recommendation or maintenance range for HGB. Both guidelines recommend that if the HGB exceeds 13 g/dL, the dose of ESA should be reduced or interrupted. In patients with CVD or complications, ESA treatment should be reduced or interrupted if the HGB exceeds 12 g/dL (Tsubakihara 2010 ; Japanese Society of Nephrology 2014).

Abbreviations: CVD = cardiovascular disease; ESA = erythropoietin stimulating agent; EU = European Union; HGB = hemoglobin; JSDT = Japanese Society for Dialysis Therapy; JSN = Japanese Society of Nephrology; KDIGO = Kidney Disease Improving Global Outcomes; NDD-CKD = non-dialysis dependent chronic kidney disease; US = United States.

The majority of patients with CKD currently receives interventional therapy in the form of iron therapy, and may initiate therapy with an ESA if other interventions fail and HGB levels fall below 9 to 11 g/dL, dependent upon local clinical practice guidelines.

A number of large, prospective, randomized controlled trials in CKD (Stages 3 to 5) have explored the potential benefit of ESAs in patients with CKD with respect to overall mortality, cardiovascular (CV) events, and progression of CKD with higher HGB targets (≥ 13 g/dL) ([Besarab et al. 1998](#); [Drüeke et al. 2006](#); [Singh et al. 2006](#); [Pfeffer et al. 2009a](#); [Pfeffer et al. 2009b](#)). These trials did not demonstrate the expected beneficial effects of correcting anemia on these outcomes, but suggested an increased risk of death and CV events when targeting higher HGB levels ([Besarab et al. 1998](#); [Drüeke et al. 2006](#); [Singh et al. 2006](#); [Pfeffer et al. 2009a](#); [Pfeffer et al. 2009b](#)). Additional analyses from these trials suggest that the risk of death or CV events appears to be highest in CKD patients who fail to respond to ESAs, as indicated by lower achieved HGB levels and higher average ESA dose requirements ([Szczecz et al. 2008](#); [Solomon et al. 2010](#)). This suggests that in some subjects the ESAs themselves, and not the HGB level, may be causative of the increase in events. This is supported by studies in CKD patients on dialysis with naturally high HGB levels and no increase in CV events ([Goodkin et al. 2011](#)).

The risks identified with ESAs from these trials have led to changes in prescribing information and practice guidelines in the US, the EU, and Japan that guide clinicians toward more cautious use of ESAs and targeting lower HGB levels. In the US, the mortality and CV risks associated with ESAs are outlined in a black-box warning in the prescribing information of ESAs with a recommendation to use the lowest dose possible to avoid transfusions. While no similar major warnings exist in the EU Summary of Product Characteristics (SmPC) or on the approved labeling for ESAs in Japan, the EU SmPCs for ESAs do suggest caution with the use of these

drugs, with a recommendation to keep HGB levels below 12 g/dL, while the Japanese practice guidelines recommend ESA treatment be reduced or interrupted if the HGB exceeds 12 g/dL in patients with CVD or complications. Further, recent EU clinical practice guidelines (Locatelli et al. 2013) recommend that risk factors for stroke (including a past history of stroke) and the presence of active malignancy or a past history of malignancy should be taken into account when making decisions to use ESAs for the treatment of anemia.

The risks associated with ESAs, including an increased risk of death and CV events, highlight the need for additional therapies that might minimize or avoid these risks when compared to currently available recombinant protein-based ESAs. Therefore, the unmet medical need for the treatment of anemia in non-dialysis dependent CKD (NDD-CKD) patients remains high, especially from a CV safety perspective. To fulfill this unmet need, the vadadustat clinical program is focused on developing an orally active therapeutic for the treatment of anemia in patients with CKD.

